**Exploratory estimand:**

CCI

**1.2. Study Design**

Overview of Study Design and Key Features	
Design Features	
 
Phase 1, open-label, single dose study to assess safety, tolerability, and PK GSK3810109 administered SC with rHuPH20 or IV in healthy adult participants. The study comprises of 2 parts.
 
Part 1 includes approximately 8 participants who will receive a single 20 mg/kg SC dose of GSK3810109 co-administered with rHuPH20.
 
Part 2 includes approximately 8 participants who will receive a single 60 mg/kg IV dose of GSK3810109. Of these 8 participants, 2 participants will comprise a sentinel cohort. The other six participants will be included in 3 different cohorts of 2 participants each that will be dosed sequentially.
 
Study duration will be up to 24 weeks excluding screening.
 
In Part 1, participants will be admitted to the clinic on day -1 and will remain in the clinic for approximately 8 hours for study-related procedures after study product administration on day 1. In Part 2, participants will be admitted to the clinic on day -1 and will remain in the clinic for monitoring for 7 days after study product administration.
 

Study Schema:
 
Part 1
  
N= 8; All participants will receive a single 20 mg/Kg SC dose of GSK3810109, and be followed up for 24-weeks
	

Overview of Study Design and Key Features	
	
Part 2
 
N= 8; All participants will receive a single 60 mg/Kg IV dose of GSK3810109, and be followed up for 24-weeks

Study intervention	Study interventions include GSK3810109 and rHuPH20. GSK3810109 is a sterile aqueous buffered solution filled into 10 mL single-dose vials. The drug dose in this study is 20 mg/kg body weight for SC infusion and 60 mg/kg body weight for IV infusion.
Study intervention Assignment	Study parts are sequential and therefore not randomized. All participants in part 1 of the study will receive a single 20 mg/kg SC dose of GSK3810109 co-administered with rHuPH20. All participants in part 2 will receive a single 60 mg/kg IV administration of GSK3810109.

## 2. STATISTICAL HYPOTHESES

There is no formal research hypothesis that will be statistically tested in this study.

### 2.1. Multiplicity Adjustment

There is no multiplicity adjustment requirement for this study.

## 3. ANALYSIS SETS

For the purposes of analysis, the following analysis sets are defined.

Analysis Set	Definition / Criteria	Analyses Evaluated
Screened	
 
All participants who will be screened for eligibility.
 
	
 
Study Population
 

Analysis Set	Definition / Criteria	Analyses Evaluated
Enrolled	
 
• All participants who sign the informed consent form (ICF).
 
• Note that screening failures (who never passed screening even if rescreened) and participants screened but never enrolled into the study (met eligibility but not needed) are excluded from the Enrolled Analysis Set as they did not enter the study.
 
	
 
• Study Population
 

Safety	
 
• All participants who receive at least 1 dose of study intervention.
 
	
 
• Safety
 

Pharmacokinetic (PK) Concentration	
 
• Participants who receive at least 1 dose of study intervention and have at least 1 assayed postdose sample of serum PK concentration data.
 
• This analysis population will be used in the assessment and characterization of PK concentrations.
 
	
 
• PK
 

Pharmacokinetic Parameter	
 
• All participants in the PK population who received study intervention for whom valid and evaluable serum PK parameters are derived.
 
• This analysis population will be used in the assessment and characterization of PK parameters.
 
	
 
• PK
 

## 4. STATISTICAL ANALYSES

Analyses will be performed separately for each study part, and will be the same across study parts, unless otherwise stated.

### 4.1. General Considerations

Participants who withdraw prior to study completion may be replaced. Schedule of activities are outlined in protocol section 1.

The final planned analysis for parts 1 and 2 will be performed after the completion of the following steps in sequence:

1. All Part 1 participants have completed the study as defined in the protocol, database cleaning is performed, and database soft lock is achieved based on complete part 1 data and all available part 2 data at this stage.
2. Interim data analysis performed for preliminary assessment of safety and PK before final analysis is performed
3. All database cleaning activities have been completed and database hard lock has been declared by the data management

The term “Analysis Set” in the SAP will be referred to as “Population: in the displays; the term “Participant” in the SAP will be referred to as “Subject” in the displays of the OPS document.

Unscheduled visits will not be included in summary tables and/or figures but will be included in determination of worst-case on study intervention/post-baseline. All unscheduled visits will be included in listings.

#### **4.1.1. General Methodology**

Unless otherwise specified, continuous variables will be summarized using n, mean, median, standard deviation, minimum, and maximum in each category. Categorical data will be summarized as the number and percentage of participants in each category. All summaries will be presented by study part, where applicable.

#### **4.1.2. Baseline Definition**

Baseline is defined as the latest pre-dose assessment with a non-missing value, including those from unscheduled visits. If time is not collected, Day 1 assessments are assumed to be taken prior to first dose and used as baseline. Unless otherwise stated, if baseline data is missing no derivation will be performed and baseline will be set to missing.

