| PIN and NRS ⁶ | | | | X | | | X | | | X | | | | | | | | | | |
| 12-lead ECG ⁷ | X | | X | | X | | X | X | X | | | | X | | | | | X | | |
| Clinical laboratory ⁵ | X | X | | | | | X | | | X | X | | X | | | X | | X | X | |
| Urinalysis ⁵ | X | X | | | | | | | | X | | | | | | | | | | |
| Pregnancy test:(serum) (POCBP only) ⁸ | X | X | | | | | X | | | X | X | | X | X | X | X | X | X | X | |
| FSH ⁹ | X | | | | | | | | | | | | | | | | | | | |
| HIV and hepatitis B and C ⁵ | X | | | | | | | | | | | | | | | | | | | |
| Test for SARS-CoV-2 ¹⁰ | X | X | | | | | | | | | | | | | | | | | | |

| Visit Number | | | 01 | 01A | 01B | 01C | 02 | 03 | 04 | 05 | 06 | 07 | 08 | 09 | 10 | 11 | 12 | 13 | ED = early discontinuation/withdrawal | |
|---------------------------------------------------------------------------|--------------------------|----------|---------------------|-------------|-----|-----|------|------|------|-----|-----|-----------|-----|-----|------|------|------|------|---------------------------------------|--|
| Time From Start of SC Infusion | | | Pre | SOI | 4hr | 8hr | 24hr | 48hr | 72hr | Wk1 | Wk2 | Wk3 | Wk4 | Wk8 | Wk12 | Wk16 | Wk20 | Wk24 | | |
| Day of Study ¹ | | D-1 | D1 | D1 | D1 | D1 | D2 | D3 | D4 | D7 | D14 | D21 | D28 | D56 | D84 | D112 | D140 | D168 | | |
| Clinical Activity | Screen Days -21 to -2 | Check-in | Intervention Period | | | | | | | | | Follow-up | | | | | | | | |
| Timed PK sample ¹¹ | | | X | X | X | | X | X | X | X | X | X | X | X | X | X | X | X | | |
| CCI [REDACTED] sample collection | | | X | | | | | | | | | | X | X | X | X | X | X | | |
| Recording of injection site reactions in 14 days diary card ¹² | | | | ←————→————— | | | | | | | | | | | | | | | | |
| Recording of AEs/SAEs ¹³ | | | | ←————→————— | | | | | | | | | | | | | | | | |
| Concomitant medication review | | | X | X | X | | X | X | X | X | X | X | X | X | X | X | X | X | | |

AE = adverse event; BMI = body mass index; COVID-19 = coronavirus disease; FSH = follicle-stimulating hormone; HIV = human immunodeficiency virus-1; ISR = injection site reaction; NRS = Numeric Rating Scale; PIN = Perception of Injection PK = pharmacokinetic(s); POCBP = participant of childbearing potential; SAE = serious adverse event; SARS-CoV-2 = severe acute respiratory syndrome-related coronavirus-2; SC = subcutaneous; SOI = start of infusion

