Visit windows: Schedule Visits 01 through 13 with respect to Day 1. Visit 01 (-10 minutes for PK sample collection and vitals; -1 hour for ECG), Visit 01A (+10 minutes); Visits 01B and 01C (\pm 10 minutes); Visits 02, 03, and 04 (\pm 6 hours); Visits 05, 06, 07, and 08 (\pm 2 days), and Visits 09, 10, 11, 12, and 13 (\pm 7 days).

- 1 Day 1 = day of product administration. The screening period will preferably be 14 days but may be extended to 21 days to allow for the possibility of study pauses or scheduling difficulty with the approval of the investigator. Day 1 evaluations prior to product administration will be considered as baseline for assessing subsequent AEs. [Note: Participants will remain in the clinic for approximately 8 hours for study-related procedures after study product administration].
- 2 Height and weight will be measured and BMI will be calculated at Screening. Only weight will be measured at Check-in and Day 1.

- 3 Vital signs will include body temperature, systolic and diastolic blood pressure, respiratory rate, and pulse. The Oxygen saturation (SPO₂) will also be measured during the in-clinic period on Day 1. For further details, refer to Section 8.1.2.
- 4 A full physical examination will be performed at Screening (at minimum, assessment of skin, head, ears, eyes, nose, throat, neck, thyroid, lungs, heart, cardiovascular system, abdomen, lymph nodes, and musculoskeletal system/extremities). A brief physical examination (at minimum, assessment of skin, lungs, cardiovascular system, and abdomen [liver and spleen]) will be performed at Check-in, at Day 1 (predose), at 8 hours, and at ED visit. Interim physical examinations may be performed at the discretion of the investigator, if necessary, to evaluate AEs or clinical laboratory abnormalities.
- 5 A complete list of assessments is provided in Section 10.2.
- 6 NRS will be administered on Day 1 at the end of the infusion. Additionally, PIN and NRS will be administered on Day 2 and Day 7.
- 7 The electrocardiogram (ECG) taken at Screening and on Day 1 before product administration will be a single reading; however, repeat ECGs are allowed at investigator's discretion to confirm the eligibility. Triplicate 12-lead ECGs will be obtained for all postdose time points.
- 8 At the Day -1 visit, a serum sample will be sent for pregnancy testing. Pregnancy testing will be conducted on POCBP only on serum samples. Refer to Section 8.1.5.

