8.1.2. Vital Signs

- Vital signs will be measured in a supine position after the participant has been at rest for at least 5 minutes in a quiet setting without distractions (e.g., television, cell phones) and will include body temperature, systolic and diastolic blood pressure, respiratory rate, and pulse.
- For Part 1, on Day 1, the vital signs and SPO₂ will be measured at predose and at 4 hours and 8 hours postdose.
- For Part 2, on Day 1, the vital signs and SPO₂ will be measured at predose, every 15 minutes from start of infusion for 2 hours, and at 4 hours and 8 hours postdose.
- For Part 3, on Day 1, the vital signs and SPO₂ will be measured at predose and at 4 hours and 8 hours postdose.

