8.1.3. Electrocardiograms

- Triplicate 12-lead ECG will be obtained in a supine position as outlined in the SoA (Section Section 1.5, Section 1.6 and Section 1.7) using an ECG machine that automatically calculates the heart rate and measures PR, QRS, QT, and QTcF intervals. The ECG taken at Screening and on Day 1 before study product administration will be a single reading; however, repeat ECGs are allowed at investigator's discretion to confirm the eligibility. Triplicate 12-lead ECG will be obtained for all postdose time points. For Part 2, for Visit 01A, ECGs will be taken within 30 minutes of EOI.

- The ECG should be read locally and be centrally archived. Please contact the Medical Monitor if any concerns.

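### The SAP's baseline fallback is not limited to records scheduled pre-dose, so an untimed post-dose Day 1 vital sign, SpO2 or ECG could become baseline

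*SAP*

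**What the plan says.** SAP 4.1.2 gives a general rule and a fallback. The general rule is: "Baseline is defined as the latest pre-dose assessment with a non-missing value, including those from unscheduled visits". The fallback follows directly: "If time is not collected, Day 1 assessments are assumed to be taken prior to first dose and used as baseline". The fallback does not mention the planned time point or the visit number.

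Protocol 8.1.2 sets the Day 1 vital signs. "For Part 1, on Day 1, the vital signs and SPO₂ will be measured at predose and at 4 hours and 8 hours postdose". In Part 2 they are "measured at predose, every 15 minutes from start of infusion for 2 hours, and at 4 hours and 8 hours postdose". For ECG, the schedules of activities mark pre-dose and 4 hours on Day 1 in both parts. Part 2 adds a reading at the end of infusion; Protocol 8.1.3 says: "For Part 2, for Visit 01A, ECGs will be taken within 30 minutes of EOI". The pre-dose ECG is a single reading, whereas after dosing the schedule notes say: "Triplicate 12-lead ECGs will be obtained for all postdose time points".

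SAP 4.3.1 plans change from baseline by time point for laboratory tests, ECG, vital signs and SpO2, and categories of maximum QTcF change with cut-points at 30 and 60 msec.

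**The concern.** Treating an untimed Day 1 record as pre-dose is safe for a measure taken only before dosing that day. It is not safe for a measure that is repeated after dosing, because an untimed later value is then declared pre-dose. As baseline is the latest pre-dose value, such a record can compete with or displace the true one.

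At stake is the description of acute effects on Day 1. Part 2 gives 60 mg/kg IV, and the protocol synopsis states that no single human dose has exceeded 40 mg/kg. With about 8 participants per part, one wrong baseline carries visible weight in a mean or a frequency table.

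**Working it through.** There is no plan figure to reproduce. The check has three steps.

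**Step 1. Count scheduled Day 1 time points for each measure with a change-from-baseline summary.** Inputs: the Part 1 and Part 2 schedules (Protocol 1.5 and 1.6), Protocol 8.1.2 and 8.1.3, and SAP 4.3.1.

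| Measure | Part | Pre-dose | After start of dosing |
|---|---|---|---|
| Vital signs, SpO2 | 1 | 1 | 2 (4 h, 8 h) |
| Vital signs, SpO2 | 2 | 1 | 120/15 = 8, plus 4 h and 8 h = 10 (11 if a time-zero reading is counted) |
| ECG | 1 | 1 (single) | 1 (4 h, triplicate) |
| ECG | 2 | 1 (single) | 2 (end of infusion and 4 h, each triplicate) |
| Laboratory, urinalysis | 1 and 2 | 0 | 0 (check-in on Day -1, then Day 2 or later) |

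Every measure with a scheduled Day 1 record also has a post-dose Day 1 record. No measure has Day 1 records that are all pre-dose, which is the case where the assumption would be safe without a further condition.

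**Step 2. Look for another rule that would prevent the error.** SAP 6.2.3 marks multiple measurements at one time point as not applicable. SAP 6.2.4 uses no visit windows. If several Day 1 records lack a time, nothing says which is the latest. Protocol 8.3 requires a 24-hour clock time for PK samples; there is no equivalent statement for vital signs or ECG.

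**Step 3. Work out the effect.** Let B be the true pre-dose value, Y(t) the value at time t, and D = Y(4 h) − B the true change at 4 hours. If the 4-hour value is used as baseline:

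- Reported change at t = Y(t) − Y(4 h) = [Y(t) − B] − D, so every change for that participant shifts by −D.
- At 4 hours the reported change is D − D = 0.
- If the effect persists at size D, later reported changes are also D − D = 0, and the effect is hidden.
- If the effect has resolved, later reported changes are 0 − D = −D, away from zero in the opposite direction.
- If M is the true maximum QTcF change, the reported maximum is M − D. It is 0 if the peak was at 4 hours, and it is inflated to M + |D| if D is negative.
- With 8 participants contributing, the mean change for the part shifts by −D/8 at each time point.

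To move a participant from the above-60 msec category to the lowest one (at most 30 msec) needs M − D ≤ 30 with M > 60, so D must exceed 30 msec.

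**The case against.** The strongest reply is that the rule is probably dormant for these measures. Its condition is that time is not collected, which most naturally means a form with no time field. The protocol allows 10 minutes before dosing for pre-dose vital signs, 1 hour for the pre-dose ECG, and 10 minutes either way at 4 and 8 hours. Adherence to such limits could hardly be checked without clock times. This stands as a reason to expect few untimed records, but it is an inference: no section says that times are recorded for vital signs or ECG, and the SAP itself provides for their absence.

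A second reply is that the visits already separate the records (01 pre-dose, 01B at 4 hours, 01C at 8 hours), and that summaries by time point need those labels anyway. A careful programmer would not use a record labelled 4 hours as baseline. That is fair, but the SAP sentence does not tell the programmer to use the labels, and its literal text points the other way. As the Part 2 schedule reads, the 15-minute readings appear only in a note and in Protocol 8.1.2, without a visit column of their own.

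Three stronger readings are tempting, and the documents do not support them:

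- *The rule acts only where it is unsafe.* It does not. An untimed Visit 01 record is correctly kept as baseline, and so is an untimed repeat ECG taken before dosing to confirm eligibility.
- *Every later change is biased toward zero.* The shift is a constant. Its effect on later changes depends on whether the Day 1 effect persists.
- *One in eight participants (12.5%) is at risk.* That figure is only the weight of one participant in a part of 8. It says nothing about how often a time is missing, and neither do the reading counts in the table.

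**Conclusion.** The gap is real and minor. A stated rule, read literally, can give a wrong baseline for vital signs, SpO2 and ECG, and no other SAP rule stops it. The consequence rests on one assumption that the documents neither state nor quantify: that some post-dose Day 1 record has no clock time. If every record is timed, the effect is nil. If one is not, that participant's change at that time point is reported as zero and the rest shift by a constant.

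The reach is limited. The primary endpoints (adverse events, injection site reactions, and Grade 2 to 4 ALT or AST) do not use this baseline. No hypothesis is tested. All vital signs and SpO2 values are to be listed, so a displaced baseline would be traceable in parts of this size, and QTcF is also categorised by its absolute maximum. A reader might infer that the safety conclusions of the study are in doubt; the documents do not support that.

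Part 3 has the same Day 1 pattern for these measures, but this SAP, based on Amendment 01, does not cover it.

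**What to change.** Replace the fallback sentence in SAP 4.1.2 with:

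*If the clock time of a Day 1 record is not available, its planned time point decides: only Day 1 records labelled pre-dose (Visit 01) may be used as baseline. Any other untimed Day 1 record, whether labelled post-dose or unscheduled with no pre-dose label, is not used as baseline.*

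The clause on unscheduled records is needed because the general rule admits unscheduled visits. Where no usable Day 1 pre-dose record exists, the general rule still falls back to the latest earlier value, such as check-in vital signs or the screening ECG.

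The cost is one replaced SAP passage. No new data are needed, since the pre-dose label already exists in the schedule. The SAP runs all safety analyses at the interim, so the change is best made before that analysis, or at the latest before the final database lock, so that it cannot look data-driven. Any SAP text written for Part 3 should carry the same wording.

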### **4.2. Primary Endpoint(s) Analyses**

#### **4.2.1. Definition of Endpoints**

The primary endpoints for this study are:

Part 1:

- The number and percentage of participants who have AEs (Grade 2 or higher) and SAEs following GSK3810109 administration through week 24.
- The number and percentage of participants who have ISRs within 7 days following GSK3810109 administration.
- The number and percentage of participants who experience Grade 2 to 4 ALT/AST following GSK3810109 administration.

Part 2:

- The number and percentages of participants who have AEs and SAEs following GSK3810109 IV administration through Week 24
- The incidence of Grade 2 to 4 elevated ALT/AST following GSK3810809 IV administration through Week 24.

#### **4.2.2. Main analytical approach**

All safety analyses will be performed on the Safety Analysis Set.

All reported AEs will be coded using MedDRA version 25.0 and summarized by system organ class (SOC) and preferred term (PT). Estimands are presented in [Section 1.1](#).

The number and percentage of participants with treatment-emergent AEs, serious AEs, study product-related AEs, deaths, and AEs leading to study product or study withdrawal through Week 24 will be provided in a summary table. Treatment-emergent AEs are defined as any AEs that occur on or after the treatment start date and time. The summary table will also include the number and percentage of participants with treatment-emergent AEs summarized by severity (grade), including (for Part 1 only) a categorization for AEs Grade 2 or higher. If treatment relationship and severity of AEs are missing, no imputation will be performed. The number and percentage of participants who have Injection/Infusion site reactions within 7 days following study treatment administration will be provided.

Separate summary tables including all AEs, study product related AEs, SAEs and adverse events of special interest (AESIs) will be generated. These summary tables will be presented by SOC, PT, and maximum grade. Grade 2 or higher AEs and common AEs will be summarized by PT. Common AEs, defined as AEs occurring in more than 5% of participants in a study part, will be presented in descending order of total incidence by PT. In summary tables which are presented by SOC and PT, SOCs will be sorted in descending order of the total incidence then alphabetically; PTs will be sorted in descending order of the total incidence then alphabetically within the SOC. For the calculations in these tables, each participant's AEs will be counted once under the maximum severity.

All AEs, AEs leading to withdrawal from the study, non-fatal SAEs, reasons for considering as a SAE, and death participant profile will be listed.

Additional details regarding AE definitions are presented in [Section 4.5.2](#).

The number and percentage of participants who have ISRs within 7 days following study product administration will be provided for parts 1 and 2. Multiple symptoms of injection site reactions will be reported as separate AEs for each reported symptom. The number and percentage of participants who have ISRs will be summarized by preferred term and by the following classifications: 'Injection Site Abscess', 'Injection Site Anesthesia', 'Injection Site Bruising', 'Injection site cellulitis', 'Injection site discoloration', 'Injection site discomfort', 'Injection site erosion', 'Injection site erythema', 'Injection site hematoma', 'Injection site hemorrhage', 'Injection site itching', 'Injection site induration', 'Injection site nodule', 'Injection site pain', 'Injection site pressure', 'Injection site soreness', 'Injection site swelling', 'Injection site tenderness', 'Injection site warmth', and 'Other'. The incidence and duration of injection site reaction AEs overall and by grade, including the time at grade, will be summarized. All ISR AEs of a participant and the corresponding length of time of events will be considered for the summary table. If there are multiple events at each grade, the length of time would be equal to the average of all event times at a grade. Participants will be included in each grade level for which they had an event.

The ISR AEs will also be summarized by each preferred term for the following variables presenting the number and percentage of participants in each category: any grade and maximum grade (1, 2, 3, 4, and 5), maximum duration (1-7, 8-14, and >14 days), outcome, and number of

events (0, 1, 2, 3, 4, 5, 6-10, 11-15, 16-20, and >20 days). In addition, an event-level summary of injection/infusion site reaction AEs by preferred term will be created which includes the following information: any grade (1, 2, 3, 4, and 5), outcome, duration, and time to onset. Duration and time to onset will be analysed as continuous variables while number and percentage will be presented for the categories of other variables.

Injection Site Reactions (ISRs)


• ISRs will be presented by preferred term and according to the following classifications:

○ Injection site abscess

○ Injection site anesthesia

○ Injection site bruising

○ Injection site cellulitis

○ Injection site discoloration

○ Injection site discomfort

○ Injection site erosion

○ Injection site erythema

○ Injection site hematoma

○ Injection site hemorrhage

○ Injection site itching

○ Injection site induration

○ Injection site nodule

○ Injection site pain

○ Injection site pressure

○ Injection site soreness

○ Injection site swelling

○ Injection site tenderness

○ Injection site warmth

○ Other injection site reactions

• Time to onset (day) of ISRs relative to injection will also be presented, where the time to onset (day) will be calculated as follows: ISR Start Date – Date of Injection + 1

• For ISR duration by grade (where grade is as specified by investigators in the eCRF), the interval between a change in grade will be assigned to the previous grade, or the grade at the start of the interval

The number and percentage of participants with Grade 2 to 4 ALT or Grade 2 to 4 AST values will be provided by study part.

